COVER PAGE

Official Title of the study: Effects of Oral Stimulation and Supplemental Nursing System on the Transition Time to Full Breast of Mother and Sucking Success in Preterm Infants: A Randomized Controlled Trial

NCT number (if available): -

Date of the document: May 2, 2018

Aim: This study aimed to investigate the effect of oral stimulation and a supplemental nursing system on the time to full maternal breastfeeding and sucking success in preterm infants. The sample consisted of 70 preterm babies.

Research Design : This longitudinal, randomized controlled study was conducted at a 21-bed level III NICU in a specialized hospital in the central district of Izmir, Turkey, between February and June 2018.

Setting and Participants: Since there was no study that used similar scales, G*POWER 3.1.9.6 program was used to calculate the sample size. GPOWER is a free statistics program that calculates sample size, power, and effect size. Statistical power analysis was used to calculate the required sample size, which indicated 26 participants were needed in each group for 80% power ($1-\beta=0.80$) with a large effect size ($d=0.80$) and a confidence interval of 95% ($\alpha=0.05$) for an analysis using t-tests (Cohen, 1988, Faul et al., 2007). We included 70 preterm infants (35 experimental, 35 control) in the study, considering sample attrition.

The inclusion criteria for the preterm infants in this study were Turkish preterm infants with (1) a birth weight of 1,000 gr and above, (2) a gestational age between 30 and 34 weeks, (3) no congenital anomaly, (4) no severe asphyxia or chronic lung disease, (5) spontaneous breathing, and (6) grades III and IV intracranial hemorrhage and no periventricular leukomalacia.

Randomization: Stratified randomization methods were used while assigning babies to control and experimental groups.

Experimental Group: Oral Motor Stimulation and an Supplemental Nursing System were applied to preterm infants in the experimental group.

Control Group: The clinic's routine feeding protocol was applied to the babies in the control group.

Follow-Up: One month after discharge, we phoned the families of the babies and were informed about their sucking status and weight after discharge.

Data Analysis: Statistical analyses were performed using the Statistical Package for the Social Sciences software for Windows, version 22.0 (SPSS, Inc., Chicago, IL, USA). A p-value of $<.05$ was significant for all analyses. Descriptive statistics were expressed as percentages, means, and standard deviations. The descriptive characteristics of the experimental and control groups were compared using chi-square and independent t-tests. Independent t-tests were used to analyze differences between the experimental and control groups in terms of transition times to oral feeding and full breastfeeding and discharge as well as gestational age and body weights at the relevant times. Independent t-tests were also used to compare the control and experimental groups in terms of mean scores of the LATCH tool. The breastfeeding status of the experimental and control groups in the first month after discharge were compared using chi-square tests. A repeated measured ANOVA test was used to compare the vital signs before, during, and after nutrition of infants in the experimental and control groups.

Ethics: Ethical approval was received from the Health Science Ethics Committee of X University. The researcher informed parents about the aim of the study and obtained written consent forms from parents. Additionally, permission from the hospital where the study was conducted was obtained.

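### Inclusion criterion (6), read literally, requires severe intracranial hemorrhage; a dropped negation is the likely cause

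*Combined protocol and SAP*

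**What the plan says.** In the combined protocol and SAP, eligibility is set out in one sentence under Setting and Participants. It opens with "The inclusion criteria for the preterm infants in this study were Turkish preterm infants with" and continues with six numbered items, each a condition for entry. Items (1) and (2) concern birth weight and gestational age. Items (3) to (5) read "3) no congenital anomaly, (4) no severe asphyxia or chronic lung disease, (5) spontaneous breathing". Item (6) reads "grades III and IV intracranial hemorrhage and no periventricular leukomalacia".

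The document has no separate list of exclusion criteria, and no other section restates who was eligible. The Aim describes the "effect of oral stimulation and a supplemental nursing system on the time to full maternal breastfeeding and sucking success in preterm infants" and does not mention hemorrhage. The Data Analysis section says "The descriptive characteristics of the experimental and control groups were compared using chi-square and independent t-tests" without naming those characteristics.

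**The concern.** Because the list is headed as inclusion criteria and each item completes the word *with*, a condition that carries no negation is one the infant must have. In item (6) the negation comes too late to reach the hemorrhage. The sentence therefore asks for infants with severe hemorrhage and without leukomalacia, while every other morbidity in the list has to be absent.

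This is the only eligibility statement available. Anyone repeating the trial, auditing enrolment or judging to whom the results apply must either follow the words and look for a population that does not fit the rest of the list, or set the words aside and infer a rule that the document does not state.

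**Working it through.** This is a check of wording. The inputs are the six numbered items under Setting and Participants.

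**Step 1: which items name a morbidity.** Items (1), (2) and (5) name none: they concern birth weight, gestational age and spontaneous breathing. Items (3), (4) and (6) name five between them.

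**Step 2: what each *no* governs.** The word occurs three times in the list.

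| Morbidity | Item | Covered by a negation? |
|---|---|---|
| Congenital anomaly | (3) | Yes, directly |
| Severe asphyxia | (4) | Yes, directly |
| Chronic lung disease | (4) | Yes, it shares the *no* through *or* |
| Grade III and IV intracranial hemorrhage | (6) | **No** |
| Periventricular leukomalacia | (6) | Yes, directly |

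The count is 1 + 2 + 0 + 1 = 4 of 5 negated, and 1 of 5 (hemorrhage) not negated.

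**Step 3: can the negation in item (6) reach back?** Compare "4) no severe asphyxia or chronic lung disease" with item (6). In item (4) the *no* stands before both conditions and *or* joins them, so it covers the pair. In item (6) the hemorrhage stands first, and a separate phrase, "and no periventricular leukomalacia", follows it. That *no* belongs to the second condition only.

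**Step 4: does another section repair it?** Hemorrhage is mentioned once in the whole document, in item (6). It does not appear in the Aim, Randomization, Experimental Group, Control Group, Follow-Up or Data Analysis sections. Exclusion criteria are mentioned nowhere. The sentence is complete and shows no gap or redaction mark that could account for a missing word.

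**Step 5: does it touch the numbers?** The stated 26 per group uses d = 0.80, α = 0.05 and 80% power. The plan does not state sidedness; two-sided is assumed here.

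- Normal approximation: n = 2(1.96 + 0.8416)² / 0.80² = 24.5, rounded up to 25.
- Noncentral t: n = 25.52, rounded up to 26, which reproduces the plan's figure.

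No input to this calculation comes from item (6), so a correction of its wording leaves both the 26 per group and the 35 per group enrolled as they are.

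**The case against.** The strongest reply is that no two statements actually conflict. An infant could in principle meet all six items as written, so this is a break in a wording pattern and an implausible reading, not a strict contradiction. Most readers would supply the missing word. The plan is written in the past tense about a study that had already included its 70 infants, so a correction would mainly tidy the record. The count of 4 in 5 describes grammar and not impact.

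Much of this stands. The problem is best called a drafting error, and the intended rule is inferred. Two further hints toward that inference are weak: the Aim's silence about hemorrhage shows little, and naming grades III and IV together is an ordinary way to describe a severity band. Item (5), which names no morbidity, does not count against item (6) either.

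The objection does not remove the defect. The rule that readers are expected to supply is the reverse of the rule that is written, and the document offers no second statement against which to check it.

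**Conclusion.** The concern holds. As written, criterion (6) makes grade III and IV hemorrhage a condition of entry, and it is the only one of the five named morbidities not required to be absent. That much can be read directly from the sentence. That a *no* was dropped is likely, because the other four morbidities all carry a negation, including the one in the same item. It remains an inference, which only the sponsor can confirm.

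The effect is confined to an accurate definition of the study population and to reproducible eligibility. The number of infants affected cannot be estimated, since the document gives no hemorrhage counts, and none is shown to be affected. The sample size and the planned analyses do not change. It should be fixed because it sits in the sole eligibility statement and costs almost nothing to put right.

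**What to change.** The sponsor should compare criterion (6) with the rest of the list and with the rule actually applied at screening, and then correct the sentence to state that rule. If absence was meant, the negation should be placed so that it covers both the hemorrhage and the leukomalacia, for example by repeating *no* before each.

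If the rule applied is confirmed and agrees with the corrected sentence, nothing further is needed. If it cannot be confirmed, or differs, the sponsor should check the enrolment records and report, by arm, any infant who does not meet the corrected criterion.

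The cost is one corrected sentence and, only in that second case, a check of the records of 70 infants. No additional patients, procedures or statistical analyses are required.

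### Allocation was stratified, but transition times and LATCH are tested by unadjusted t-tests: a valid analysis that loses precision if the strata or gestational age explain more than a small share of outcome variance

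*Combined protocol and SAP*

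**What the plan says.** The Randomization paragraph is one sentence: "Stratified randomization methods were used while assigning babies to control and experimental groups". It names no factors, levels or block size.

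Under Data Analysis, for transition times, "Independent t-tests were used to analyze differences between the experimental and control groups"; for breastfeeding performance, "Independent t-tests were also used to compare the control and experimental groups in terms of mean scores of the LATCH tool". Baseline characteristics are compared between arms and not used further. The phrase "as well as gestational age and body weights at the relevant times" adds more between-arm comparisons, not an adjustment. No ANCOVA, regression or stratified test appears for these outcomes.

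Setting and Participants states that "26 participants were needed in each group for 80% power" at d = 0.80, "for an analysis using t-tests". It then says: "We included 70 preterm infants (35 experimental, 35 control) in the study, considering sample attrition". The large standardised effect was adopted because of a lack of precedent: "Since there was no study that used similar scales".

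**The concern.** Stratifying is normally worthwhile because the factors are thought to predict outcome. If they do, an analysis that ignores them can lose in two separate ways:

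- **Precision.** Outcome variance that baseline variables could explain stays in the error term, however allocation was done.
- **Calibration.** If allocation was balanced within prognostic strata, the true sampling variance of the difference falls but the t-test standard error does not reflect this. The interval is then too wide and the test conservative.

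Gestational age and birth weight are eligibility criteria, so both are known at entry. The trial is small and its effect size is a convention, so precision could matter if the true effect is below d = 0.80.

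**Working it through.** **Inputs from the documents.** d = 0.80, alpha 0.05, 80% power, 26 per group needed, 35 per group included, t-test (Setting and Participants; Data Analysis). Sidedness is not stated; two-sided reproduces the plan's figure.

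**Assumed, because the documents are silent.** R2, the share of outcome variance explained by gestational age, is shown as a range. The 30 to 34 week window may keep it low, and it may differ between outcomes.

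**Step 1: the plan's own figure.** Two-sided two-sample t-test, noncentrality d × √(n/2), df = 2n − 2:

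- n = 25: 0.80 × √12.5 = 2.83, power 79.1%
- n = 26: 0.80 × √13 = 2.88, power 80.7%, so 26 is reproduced
- n = 35: 0.80 × √17.5 = 3.35, power 91.0%
- n = 35, assumed d = 0.50: 0.50 × √17.5 = 2.09, power 54.1%

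With 35 per arm, 80% power needs d of about 0.68 or more.

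**Step 2: when adjustment pays.** Without balance within strata, k covariate terms multiply the variance of the estimated difference by (1 − R2) × (N − 3)/(N − 3 − k). This equals 1 at R2 = k/(N − 3).

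| Covariate terms | 35 per arm (N = 70) | 26 per arm (N = 52) |
|---|---|---|
| 1 | 1/67 = 0.015 | 1/49 = 0.020 |
| 2 | 2/67 = 0.030 | 2/49 = 0.041 |
| 3 | 3/67 = 0.045 | 3/49 = 0.061 |
| 5 | 5/67 = 0.075 | 5/49 = 0.10 |

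Below these values the adjusted model is the less precise one.

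**Step 3: size of the gain.** Simulation, 8,000 trials per cell. Gestational age is uniform over 30 to 35 weeks with a linear effect; birth weight correlates 0.6 with it and adds nothing; errors are normal. The adjusted model has three terms: a two-level stratum, gestational age and birth weight. Schemes: A, strata cut at 32 weeks with blocks of 4; B, no balance within strata; C, blocks of 4 in a non-prognostic stratum. Power (%), t-test vs adjusted, 35 per arm, d = 0.80:

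| R2 | A | B | C |
|---|---|---|---|
| 0 | 90.6 vs 89.7 | 91.0 vs 89.7 | 91.0 vs 90.1 |
| 0.05 | 91.0 vs 91.2 | 91.1 vs 91.2 | 91.2 vs 91.8 |
| 0.10 | 91.9 vs 93.0 | 90.9 vs 92.3 | 90.9 vs 92.9 |
| 0.20 | 92.6 vs 95.1 | 90.7 vs 94.9 | 91.0 vs 95.5 |

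Hand check at R2 = 0.20: √(0.80 × 67/64) = 0.915, so the detectable d falls from 0.68 to 0.68 × 0.915 = 0.62.

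At an assumed d = 0.50, scheme A gives 54.2 vs 57.3 at R2 = 0.10 and 53.0 vs 60.4 at 0.20; in B and C the gain at 0.20 is 7 to 9 points. At 26 per arm and d = 0.80, scheme A gives 81.3 vs 79.4 at R2 = 0 and 82.5 vs 87.0 at 0.20. With skewed (lognormal) errors, scheme A at 35 per arm and d = 0.80, the R2 = 0.20 comparison is 91.2 vs 93.2.

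**Step 4: conservatism under scheme A.** The variance of gestational age is 25/12 = 2.083. Strata holding 40% and 60% of infants, with means 31 and 33.5, carry 0.4 × 0.6 × 2.5² = 1.5 of it, or 72%. At R2 = 0.20 the stratum explains 0.72 × 0.20 = 0.144 of outcome variance. With perfect balance the t-test standard error would be too large by 1/√0.856 = 1.08; with incomplete blocks the simulation gives about 1.07. The critical value is then effectively 1.96 × 1.07 = 2.10, a two-sided error of about 3.6%. In B and C the t-test holds its level (4.5 to 5.2%).

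**The case against.** The strongest defence is that the plan is coherent: it sizes the trial for a t-test and uses a t-test. At its design point power is already 91%. The strata are unnamed, nothing in the documents says gestational age or birth weight predicts these outcomes, and R2 is wholly assumed. All of that stands, and it limits this point to a suggestion. For the same reason, gains at R2 of 0.36 or 0.50 should not drive any decision.

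It is also fair that a model with stratum, gestational age and birth weight can be heavier than needed. In a separate run, arm plus gestational age alone gave 84.7% against 83.5% for three terms (26 per arm, scheme A, R2 = 0.10, d = 0.80). The fix below is lighter for that reason.

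A reader might infer three stronger things, none of which the documents support:

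- **That the t-test is invalid or the sample size wrong.** Randomisation protects the unadjusted comparison. There is no bias and no type I inflation, and 26 per group reproduces.
- **That precision is lost whenever a baseline variable predicts outcome at all.** Step 2 shows the association must exceed break-even. In scheme B at 26 per arm and R2 = 0.05, the t-test has 80.6% power and the three-term model 80.1%.
- **That gestational age or birth weight were the strata, or that the intervals are definitely too wide.** Neither factors nor blocking are given, so the conservatism in step 4 is only a possibility.

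What the defence does not answer is that d = 0.80 is a convention, not evidence. At a smaller true effect the same R2 is worth more.

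**Conclusion.** The mismatch between the stratified design and the unstratified analysis is real. Its consequence is possible inefficiency, not an error of validity. The change is worth considering, with medium confidence.

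At the plan's design point the benefit is about nil at R2 = 0.05 and modest up to 0.20. It becomes material mainly if the true effect is well below d = 0.80 and R2 is near 0.20 or more. These sizes rest on the assumed R2, a linear gestational-age effect, and the assumed strata and block size. They come from a three-term model; with no added information in birth weight, dropping it would do slightly better. The one gap that holds whatever R2 is: without the strata and blocking, a reader cannot tell whether the planned t-test is exact or conservative.

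**What to change.** 1. State the stratification factors, their levels and the blocking.
2. For transition times and LATCH, fit a linear model with arm, the actual randomisation strata from the allocation record, and gestational age at entry as a continuous covariate. Add birth weight only if it was a stratification factor or was prespecified as prognostic. With many strata, check the number of terms against the break-even table.
3. Make the adjusted difference with its 95% CI the main result only if the model is fixed, with a dated record, before outcomes are examined; otherwise report it as supportive. Give the unadjusted difference alongside in both cases. The dated record matters because the document carries a date of May 2, 2018, inside the February to June 2018 study period.

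**Cost.** A change of wording and retrieval of the strata; no new data, since gestational age is needed for eligibility. The statistical price is a few degrees of freedom and, if nothing is prognostic, about 1 point of power at 35 per arm or about 2 at 26 per arm (d = 0.80, three terms). Like the t-test, this model needs an observed transition time for every infant, so it does not settle how unreached times are handled.

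### One p<.05 rule covers every analysis, while the aim's two outcomes are unranked and the sample size is tied to neither

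*Combined protocol and SAP*

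**What the plan says.** **Aim.** The study examines the effect of the two interventions "on the time to full maternal breastfeeding and sucking success in preterm infants". The title pairs the same two outcomes. Neither place calls one of them primary.

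**Setting and Participants.** The calculation opens with "Since there was no study that used similar scales" and concludes that "26 participants were needed in each group for 80% power", using a large effect (d = 0.80), alpha 0.05 and t-tests. It names no outcome. Enrolment was then set higher: "We included 70 preterm infants (35 experimental, 35 control) in the study, considering sample attrition".

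**Data Analysis.** The significance rule is "A p-value of $<.05$ was significant for all analyses". Independent t-tests compare the arms on "transition times to oral feeding and full breastfeeding and discharge as well as gestational age and body weights at the relevant times", and also "in terms of mean scores of the LATCH tool". Breastfeeding status one month after discharge is compared by chi-square, and vital signs by repeated-measures ANOVA. The section gives no order of testing, division of alpha or adjustment.

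**Measure of sucking success.** The documents do not say which measure this is. LATCH is one candidate. The Follow-Up section also collects sucking status by telephone at one month.

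**The concern.** The 5% and 80% in the sample size describe a single t-test. The aim has two outcomes, and the decision rule lets either be declared significant at 0.05. A reader who takes significance on either one as a positive trial is accepting more than a 5% chance of a false difference on the trial's own aim. That reader also cannot tell whether time to full breastfeeding or sucking success was the outcome the calculation was made for.

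This goes beyond a missing detail, because the plan states a rule. Followed as written, it gives every listed comparison the same standing as the two outcomes in the aim.

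**Working it through.** **Inputs.** From Setting and Participants: d = 0.80, alpha 0.05, 80% power, 26 per arm needed, 35 per arm enrolled. From Data Analysis: 0.05 for each test. From the aim: two outcomes. The correlation between the two test statistics is not in the documents, so it is varied.

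**1. Reproduce the plan's figure.** Two-sided t-test power uses 2n − 2 degrees of freedom and noncentrality d × √(n/2).
- n = 25: power 79.1%.
- n = 26: noncentrality 0.80 × √13 = 2.88, power 80.7%.
- n = 35: noncentrality 0.80 × √17.5 = 3.35, power 91.0%.

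So 26 per arm is correct for one two-sided test at 0.05. The plan does not state sidedness, but a one-sided test would need only 21 (79.9% at 20, 81.7% at 21).

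**2. Error over the two aim outcomes.** Assume no true difference on either outcome, one test each, and significance on either counted as success. Then

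P(at least one) = 1 − P(|Z₁| < 1.96 and |Z₂| < 1.96).

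Under independence this is 1 − 0.95² = 0.0975. For a benefit-direction claim, P = 1 − P(Z₁ < 1.96 and Z₂ < 1.96), which under independence is 1 − 0.975² = 0.049. Other values come from the bivariate normal distribution.

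| Assumed correlation | Any false difference | Benefit direction only |
|---|---|---|
| 0 | 9.75% | 4.9% |
| 0.5 | 9.1% | 4.5% |
| 0.7 | 8.3% | 4.2% |
| 0.9 | 7.0% | 3.5% |
| 0.95 | 6.5% | – |
| One test only | 5% | 2.5% |

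Simulated t-tests at 35 per arm agree: 9.7%, 9.2% and 7.1% at correlations 0, 0.5 and 0.9. The error tends to 5% as the correlation approaches 1.

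**3. What a fixed order costs.** The primary is still tested at 0.05, so its power is as in step 1. The second outcome can be claimed only when both tests are significant. If both are continuous with d = 0.80, independence gives 0.8075² = 0.652 at 26 per arm and 0.9097² = 0.828 at 35. Simulation gives the correlated cases.

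| Per arm | Ungated | Gated, correlation 0 | 0.5 | 0.9 |
|---|---|---|---|---|
| 26 | 81% | 65% | 70% | 76% |
| 35 | 91% | 83% | 85% | 88% |

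**4. The alternative of splitting alpha.** At 0.025 for each outcome, power is 71.6% at 26 per arm and 85.2% at 35. Reaching 80% would take 31 per arm.

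**The case against.** **The error rates are conditional.** If one outcome truly differs, the chance of a false claim on the other is 5%. If both had to be significant, the error would be at most 5%. If the two are separate questions, each keeps its own 5%. All of this stands, so 7% to 10% cannot be read as the trial's unconditional false-positive rate. The documents state none of these success rules, however, and the one rule they do state permits a claim on either outcome.

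**The generic effect size fits any continuous outcome.** Linking d = 0.80 to a named outcome would change no number in the calculation. That is true, and the arithmetic is sound. The link still matters, because it would show which outcome the trial was sized to answer.

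**LATCH is the obvious measure of sucking success, and the mention of scales points to it.** A reader might infer this, but the documents never say so. If the measure is instead one-month sucking or breastfeeding status, the outcome may be categorical, and the t-test power figures for the second outcome do not apply.

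**No primary outcome was ever prespecified.** A reader might infer this too. The documents show only that this short summary names none; an earlier record may exist.

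**The long list of tests makes the error far larger.** The documents do not support a figure. The number of tests is undefined, their correlations are unknown, and they are not equal claims: age and weight at a milestone depend on its timing, and vital signs are not in the aim.

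**Conclusion.** The point holds in conditional form. The plan makes p<.05 significant throughout, ranks neither outcome in its aim, and ties its sample size to neither. The excess over 5% in the working depends on three conditions: no true difference on either outcome, one test per outcome, and either result alone counted as success. Under those conditions the error is nearly doubled at most, and the excess shrinks as the correlation rises. For false claims of benefit the figures are about half as large.

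The sample-size arithmetic is right; what it lacks is a named outcome. The wording should be changed, but nothing here shows that the trial was too small or that any result is false.

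**What to change.** **Testing rule.** Replace the blanket significance rule with one primary outcome at two-sided 0.05. Test the other aim outcome at 0.05 only if the primary is significant.

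**Choice of primary.** Use the outcome for which the sample size was calculated. If it was calculated for neither, the sponsor should choose one and say that d = 0.80 is generic. Time to full breastfeeding, named first in the title and aim, is a reasonable default, though that is a preference and not something the documents settle.

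**Definition and reporting.** State which single measure is sucking success: LATCH, or one-month sucking or breastfeeding status. Report the other comparisons with 95% confidence intervals as supportive.

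**Timing.** Date the designation and state whether outcome data had been seen. The cover page reads "Date of the document: May 2, 2018", within the February to June 2018 study period, and the text is in the past tense. If data had been seen and no earlier record names a primary, label the choice post hoc and claim no trial-wide 5% error control. The gain is then honest disclosure only.

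**Cost.** No extra infants and no loss of power for the primary. The second outcome loses power as in step 3 of the working, if it is continuous with d = 0.80. Isolated significant results among the supportive comparisons could no longer be presented as findings.
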